Endpoints:	Primary endpoint 
Objective response rate (CR+PR) within the first 48 weeks (12 cycles) of therapy, using RAPNO criteria Secondary endpoints: 
PFS at 12, 24 and 60 monthsBest response rate (CR+PR) within 24 cycles of therapyClinical benefit response rate (CR+PR+MR+SD) after 12 and 24 cycles of therapyPoly-ICLC-related toxicities Exploratory endpoints 
Vision response after 12 and 24 cycles of therapy defined as 0.2 logMAR or greater in acuity improvementPatient reported outcomes and quality of life measuresBiological correlatesComparison of RANO and RAPNO response determinations
Accrual Objectives:	Up to 20 participants will be enrolled to obtain a minimum of 16 evaluable participants on this study.
Study Duration:	Participants will be followed for a minimum of 5 years from treatment. Overall survival outcomes will continue to be measured up to 5 years from treatment.
Interim Analysis:	There will not be an interim analysis for efficacy.

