In addition, on this study, the research monitor is specifically required to review all unanticipated problems involving risk to participants or others, serious adverse events and all participant deaths associated with the protocol and provide an unbiased written report of the event. At a minimum, the research monitor should comment on the outcomes of the event or problem, and in the case of a serious adverse event or death, comment on the relationship to participation in the study. The research monitor should also indicate whether he/she concurs with the details of the report provided by the study investigator.

Safety Monitoring Criteria

Table 14 below defines the maximum allowed number of Grade 4 adverse events that are at least possibly attributable to the study drug.

If the number of events exceeds the number in the second column, accrual to the study should be placed on hold for safety evaluation, pending review of toxicities by the study committee in consultation with the DSMB and the research monitor, to determine whether the study should continue, be amended, or be terminated. For example, if 2 or more patients experience an event before the sixth patient begins therapy, the trial will be on hold.

Table 14. Safety Rules for Grade 4 Adverse Events

Number of Patients	Maximum Number Permitted	Probability to Stop	Cumulative Probability to Stop
5	1	0.081	0.081
10	2	0.070	0.151
16	3	0.068	0.219

Statistical Justification: The trial should hold enrollment and have a DSMB evaluation for safety if the probability that a Grade 4 adverse event (defined above) exceeds 10% is equal to or higher than 0.95, i.e., stop if $\Pr\{\Theta > 0.10 | \text{data}\} \geq 0.95$. The table above gives the safety rule for each set of 5 participants that enrolls in the study, with column 2 indicating the maximum number of cases of events that are permitted. The third column gives the probability of holding enrollment on the trial when in fact, the true $\Theta = 0.10$. Safety rules were generated using a binomial distribution.

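### Table 14's cumulative probability of a safety hold should read 0.113 and 0.137, not 0.151 and 0.219, and Section 12 does not settle whether events or patients are counted

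*Combined protocol and SAP*

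**What the plan says.** Section 12, Safety Monitoring Criteria, introduces Table 14 as one that "defines the maximum allowed number of Grade 4 adverse events that are at least possibly attributable to the study drug". The table has three rows, and its last column is headed "Cumulative Probability to Stop":

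| Patients | Maximum permitted | Probability to stop | Cumulative |
|---|---|---|---|
| 5 | 1 | 0.081 | 0.081 |
| 10 | 2 | 0.070 | 0.151 |
| 16 | 3 | 0.068 | 0.219 |

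The trigger reads "If the number of events exceeds the number in the second column, accrual to the study should be placed on hold for safety evaluation". The worked example puts the trial on hold "if 2 or more patients experience an event before the sixth patient begins therapy". The statistical justification describes column 2 as the "maximum number of cases of events that are permitted". It states that column 3 is calculated at a true rate of 0.10 and that "Safety rules were generated using a binomial distribution". It bases the rule on a posterior probability of at least 0.95 that the rate exceeds 10%, and names no prior.

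On the timing of looks it says: "The table above gives the safety rule for each set of 5 participants that enrolls in the study". The Protocol Summary (Accrual Objectives) says: "Up to 20 participants will be enrolled to obtain a minimum of 16 evaluable participants on this study".

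**The concern.** Two things looked wrong.

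First, column 4 equals the running total of column 3. That would be a cumulative probability only if a trial could cross the limit at one look at most. The counts are nested, so a trial over the limit at 5 patients is often still over it at 10 or 16, and the sum counts it again. Anyone reading the table would take the rule to be more prone to false holds than it is.

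Second, the section uses two counting units. A binomial calculation needs each patient to count at most once, but the lead-in and the trigger are worded in events. Section 6.4 allows restart after Grade 3 or 4 events and provides for a patient who has another one, so repeats within a patient are foreseen. At stake is whether sites, the DSMB and the research monitor reach the same hold decision from the same data.

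A lesser mismatch is that the text describes looks every five participants, while the rows are 5, 10 and 16 and enrolment may reach 20.

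**Working it through.** **Inputs**, all from Section 12: true rate p = 0.10; looks at n = 5, 10 and 16; hold if the count exceeds 1, 2 and 3.

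**Column 3 reproduces.** With X ~ Bin(n, 0.10):
- P(X ≥ 2 | n = 5) = 0.0815
- P(X ≥ 3 | n = 10) = 0.0702
- P(X ≥ 4 | n = 16) = 0.0684

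These are the printed 0.081, 0.070 and 0.068. Each is the unconditional tail at its own look.

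**Column 4 is the sum.** 0.081 + 0.070 = 0.151, and 0.151 + 0.068 = 0.219. Treating the looks as independent would give 0.146 and 0.204, so that does not explain the printed figures either.

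**Exact cumulative probability.** Carry forward only trials not yet held. Let X₅ be the count in patients 1–5, Y ~ Bin(5, 0.10) the count in patients 6–10, and Z ~ Bin(6, 0.10) the count in patients 11–16.

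- Look 1: 0.0815.
- First hold at look 2: P(X₅=0)·P(Y≥3) + P(X₅=1)·P(Y≥2) = 0.59049×0.00856 + 0.32805×0.08146 = 0.0318.
- Not held by patient 10, by count: 0 events 0.34868, 1 event 0.38742, 2 events 0.15066 (total 0.88676).
- First hold at look 3: 0.34868×P(Z≥4) + 0.38742×P(Z≥3) + 0.15066×P(Z≥2) = 0.34868×0.00127 + 0.38742×0.01585 + 0.15066×0.11427 = 0.0238.
- Cumulative: 0.0815, 0.1132, 0.1370.

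**Cross-check by overlaps.** The chance of being over the limit is 0.0384 at both 5 and 10, 0.0281 at 5 and 16, 0.0397 at 10 and 16, and 0.0232 at all three. Then 0.2201 − (0.0384 + 0.0281 + 0.0397) + 0.0232 = 0.137. A simulation of 2,000,000 trials gave 0.081, 0.113 and 0.137. Checking after every patient, with each row's limit applied to the patients leading up to it, also gives 0.137 by patient 16.

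**Size.** 0.151 − 0.113 = 0.038 and 0.219 − 0.137 = 0.082; the ratios are 1.33 and 1.60.

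**Counting unit.** Suppose one of the first five patients has two qualifying events and the others have none. Counting events gives 2 > 1, a hold. Counting patients gives 1, no hold. The documents give no repeat rate, so the following is an assumption: each patient has a qualifying event with probability 0.10, and a share q of affected patients has a second. With events counted, the same recursion gives a hold probability by patient 16 of 0.197 (q = 10%), 0.277 (25%) or 0.393 (50%), against 0.137 when patients are counted.

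**Looks.** With limit 3 the tail at n = 15 would be 0.056, so the printed 0.068 was calculated at 16 and does not belong to a third set of five. The posterior rule does not fix a limit at 20. Beta(1,1) and Beta(1.1,1) priors both reproduce the limits 1, 2 and 3, but at 4 of 20 their posterior probabilities are 0.948 and 0.953, on opposite sides of 0.95.

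**The case against.** The strongest reply is that column 4 decides nothing. Holds are triggered by column 2, the text explains only columns 2 and 3, and the error overstates the false-hold risk, so it loosens no protection. A hold is also a pause for review and may end in continuation. All of this is correct. It makes the arithmetic a small correction, and the ratio of 1.6 applies to the last row only.

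On the counting unit, the first column is headed by patients, the calculation is binomial, and the only worked example counts patients, so a careful reader would probably settle on patients. That is fair, but the operative trigger sentence still says events, and someone applying it literally would reach a different decision.

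The assumed repeat rates have no source in the documents. They show direction and range, and the point does not depend on them; the two-event example is enough.

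On enrolment, a limit first applied at 20 would leave no accrual to hold, and 16 is the planned evaluable sample, which plausibly explains the last row. Research-monitor review of serious events and deaths (Section 12) and continuous toxicity monitoring (Section 14.3) also cover patients 17 to 20. What remains is a mismatch between text and table; oversight is not absent.

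**Conclusion.** The concern holds. At a true rate of 0.10, with independent patients each counted once, the cumulative hold probabilities are 0.081, 0.113 and 0.137. The printed 0.151 and 0.219 are wrong as cumulative probabilities. This part is exact and needs no assumption beyond those the plan states.

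The inconsistent counting unit is the part that can change a decision, since identical data can give a hold or no hold. How often that would happen cannot be determined from the documents.

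The limits in column 2 and the probabilities in column 3 stand. The correction should be made, but nothing here suggests that the safety rule is unsafe.

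**What to change.** 1. In Table 14, change the cumulative column to 0.081, 0.113, 0.137.
2. Reconcile the lead-in, trigger, worked example and justification to one counting unit. Patients with at least one qualifying Grade 4 event is the unit under which the printed probabilities are valid. If the sponsor intends to count events, columns 3 and 4 would have to be recalculated under a stated repeat rate.
3. Reconcile the description of looks every five participants, and enrolment of up to 20, with rows at 5, 10 and 16, and state the prior behind the 0.95 rule. No limit for patients 17 to 20 and no prior is proposed here.

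The cost of the first two items, if patients are the unit, is two table cells and a few sentences, with the printed limits unchanged. The third could add a row if the sponsor chooses. The change goes to the IRB as an amendment under Section 13.1. Because it clarifies a safety-hold rule, the sponsor should also check whether the DoD/OHRO approval described there applies.

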Based on the safety analysis set, information regarding study treatment administration, drug dosing and cycle compliance, safety variables, will be described and summarized. Data from the biological analysis will also be described and summarized. Safety will be assessed via tabulations of AEs and SAEs as well as Diary recordings following treatment dose/cycle of therapy.

All analyses for outcome results will be based on evaluable participants, as defined in section 14.

At the end of the trial, we will report poor performance if the treatment is rejected when not meeting the criteria of at least 3 responders' cases. If there is no success, we will report a failure to reject the null hypothesis. If the null hypothesis is rejected, the probability of the estimated success rate will be reported and 95% confidence intervals as well as the distribution of changes in tumor size.

Dose-limiting toxicity (DLT) is not an objective in this trial. Toxicity will be continuously monitored.

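### Table 14 and the posterior hold criterion in Section 12 agree at 5, 10 and 16 patients but can disagree between those counts, and no prior is stated to settle which limit applies

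*Combined protocol and SAP*

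**What the plan says.** Section 12 (Safety Monitoring Criteria) gives a hold rule for Grade 4 events at least possibly attributable to the drug, in two forms.

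- **A posterior criterion**, under the statistical justification: "The trial should hold enrollment and have a DSMB evaluation for safety if the probability that a Grade 4 adverse event" rate, theta, "exceeds 10% is equal to or higher than 0.95". It is not restricted to particular patient counts, and no prior for theta is given. The text says only that the rules came from a binomial distribution.
- **Table 14**, with columns for patients, maximum permitted, probability to stop at theta = 0.10, and cumulative probability: "5 1 0.081 0.081"; "10 2 0.070 0.151"; "16 3 0.068 0.219". The trigger is "If the number of events exceeds the number in the second column, accrual to the study should be placed on hold".

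Two remarks bear on how the rows apply between 5, 10 and 16. The table "gives the safety rule for each set of 5 participants", which suggests batches. The worked example, however, has the trial go on hold if two or more patients have an event before patient 6 starts, which applies the first row as a limit over patients 1 to 5. Section 14.3 adds "Toxicity will be continuously monitored". Section 14.2 allows up to 20 participants, but the table ends at 16.

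**The concern.** A study team that sees a second qualifying Grade 4 event in patient 6 or a third in patient 11 has two instructions. Read as a band, the table permits the count. Read as written, the criterion may require a hold. Nobody can settle this from the protocol, because a posterior probability cannot be computed without a prior. At stake is a hold on accrual for safety review that comes later than the plan's own criterion would give, in patients under 22 with no lower age limit. The printed cumulative probabilities, which a DSMB would use to judge how often the rule fires, need checking as well.

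**Working it through.** **Inputs.** From Section 12: theta limit 0.10, posterior threshold 0.95, and maximum permitted 1, 2, 3 at n = 5, 10, 16. Assumed, because the protocol is silent: the prior, and rows read as bands (1–5, 6–10, 11–16).

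**1. The table's own figures.** Column 3 is P(X ≥ max + 1), X ~ Bin(n, 0.10):
- n = 5, X ≥ 2: 0.0815 (printed 0.081)
- n = 10, X ≥ 3: 0.0702 (printed 0.070)
- n = 16, X ≥ 4: 0.0684 (printed 0.068)

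Column 3 reproduces. The cumulative column is a plain sum: 0.081 + 0.070 = 0.151, and 0.151 + 0.068 = 0.219. These events overlap, so the sum overstates the cumulative probability. By patient 10 the exact value is 1 − P(X5 ≤ 1 and X10 ≤ 2) = 1 − (0.59049 × 0.99144 + 0.32805 × 0.91854) = 0.113. The same recursion to 16 gives 0.137. Looks-only and band readings give the same values at the rows, since a count over the limit inside a band is still over it at the band's end.

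**2. Criterion at the tabulated counts.** With a Beta(a, b) prior, Pr(theta > 0.10 | x, n) = 1 − BetaCDF(0.10; a + x, b + n − x).

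| Prior | 1/5, 2/10, 3/16 (permitted) | 2/5, 3/10, 4/16 (hold) |
|---|---|---|
| Uniform (1, 1) | 0.886, 0.910, 0.917 | 0.984, 0.981, 0.978 |
| Jeffreys (0.5, 0.5) | 0.802, 0.857, 0.876 | 0.971, 0.969, 0.965 |

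Both priors reproduce the table at all three rows.

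**3. Criterion between the rows.** Under the uniform prior the posterior equals P(Bin(n + 1, 0.10) ≤ x). For 2/6 this is 0.4783 + 0.3720 + 0.1240 = 0.974.

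| Count permitted by the bands | Uniform | Jeffreys |
|---|---|---|
| 2/6 | 0.974 | 0.954 |
| 2/7 | 0.962 | 0.934 |
| 3/11 | 0.974 | 0.957 |
| 3/12 | 0.966 | 0.944 |
| 3/13 | 0.956 | 0.930 |

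Under the uniform prior the criterion is no longer met at 2/8 (0.947) or 3/14 (0.944). At the very start, 1/1 meets it under both priors (0.990 and 0.986), and 1/2 under the uniform prior only (0.972).

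**4. Sensitivity to the prior.** On a grid of a = 0.1–2 and b = 0.1–10, 672 priors reproduce all three rows. Among them 3/11 meets the criterion in 92%, 2/6 in 73%, 2/7 in 49% and 3/13 in 47%. For 29 of the 672 no permitted count meets it at any n.

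**5. Consequence at an assumed true rate of 30%.** With bands, a hold by patient 7 needs two events in the first five (0.472), or one in the first five and then both of the next two (0.360 × 0.09 = 0.032), so 0.50. With the uniform-prior criterion from patient 3 it needs two events in seven: 1 − 0.7^7 − 7 × 0.3 × 0.7^6 = 0.67. Exact recursion at later counts gives 0.67 against 0.73 by patient 10, 0.71 against 0.83 by 13, and 0.81 against 0.86 by 16.

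**6. Price at a true rate of 10%, over 16 patients.** Bands 0.137; uniform-prior criterion from patient 3, 0.205; from patient 1, 0.298.

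**The case against.** The strongest reply is that the design is batched. The posterior statement is offered as justification, the table is described per set of five, and the limits are right at each tabulated count. On that reading nothing contradicts. The Section 14.3 sentence on continuous monitoring follows a remark on dose-limiting toxicity and may mean ordinary adverse event surveillance. This reading is available, but it leaves no limit at all between looks, and the worked example points the other way.

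A second reply is that the list of conflicting counts depends on the reviewer's prior. That stands: under Jeffreys three of the five drop out, and under Beta(1/3, 1/3), which also reproduces the rows, all five do. A third is that applying the uniform-prior criterion at every patient would also hold for a single event in the first one or two patients, which sits badly with an example that requires two. That stands too, and is why a minimum number treated must be stated.

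Other oversight also limits the harm. The research monitor reviews serious adverse events and can stop the study, a DSMB monitors the trial, Section 6.4 interrupts drug for Grade 4 events suspected to be related, and the rule triggers review, not termination.

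A reader might infer that Table 14 is simply laxer than the criterion, or miscalculated. The documents do not support that. Column 3 reproduces, the limits agree at 5, 10 and 16 under two standard priors, and some priors consistent with the table give no conflict. Under Beta(1, 9) the table would even be stricter than the criterion (0.842 at 2/5, 0.885 at 3/10, 0.902 at 4/16), although that prior then fails to reproduce the table.

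**Conclusion.** The criterion and the table are not reconciled between the tabulated counts. Given the band reading, the conflict at 2/6 and 3/11 holds under both standard priors examined; at 2/7, 3/12 and 3/13 it needs the uniform prior. The practical gap is moderate and local: 0.50 against 0.67 for a hold by patient 7 at a 30% rate, narrowing to 0.81 against 0.86 by patient 16. Those figures rest on the uniform prior, on starting at patient 3, and on a 30% rate that the protocol does not give. Independently of any prior, the cumulative column is wrong as a cumulative probability: 0.113 and 0.137 should stand where 0.151 and 0.219 are printed.

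**What to change.** Revise Table 14 and its justification.

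- State the prior and the minimum number treated before the rule applies.
- Print the limit that follows from the criterion for every count up to the 20 who may enrol. Under a uniform prior from patient 3 that would be a hold at 2 events for 3–7 patients, 3 for 8–13, 4 for 14–19 and 5 at 20. Another prior gives another list; the choice belongs to the sponsor and the DSMB.
- If looks only at 5, 10 and 16 are intended, say so, and say what governs between them and from 17 to 20.
- Recompute the stop probabilities, with the cumulative column by exact recursion.

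This is one replacement table and a few sentences. The cost is more false holds: over 16 patients at a true 10% rate, 0.205 from patient 3 instead of 0.137, or 0.298 if the rule starts at patient 1. The 0.205 is below the 0.219 that the protocol already prints.

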4.2. Treatment Dosing Options

Table 4: Recommended Dosing Options

	Option 1*	Option 2*
Monday	X	
Tuesday		X
Wednesday		
Thursday	X	
Friday		X
Saturday		
Sunday		

X= drug administration. Cycles are 28 days

*If a participant misses a dose of medication on the scheduled day, a dose can be given up to 24 hours later. Injections must be separated by at least 48 hours.

Participants will receive poly-ICLC 20 mcg/kg/dose twice weekly IM (using Monday/Thursday or Tuesday/Friday schedule if possible). The first dose will be administered in the clinic under supervision. To facilitate processing of biological samples, samples should not be obtained on a Friday.

Participant will be monitored 1 hour (+/- 30 minutes) after the first dose. For all subsequent cycle 1 doses administered at home, a log will be kept documenting the temperature of the participant before study drug administration and 12 hours (+/- 6 hours) after study drug administration. After cycle 1, temperature will only be monitored on an as needed basis, such as if the participant is not feeling well. Participants or their parents will be instructed to use a log to record the temperature monitored at home and any fever > 39⁰ Celsius should be recorded on the log.

Participant or parent will receive appropriate teaching by the medical team for intramuscular injections administration. After the first dose if family and medical team feel comfortable, then the rest of the medication will be administered at home. The study drug will be dispensed to the participant/parent/guardian by the institutional research pharmacy. The study drug will be dispensed in vials along with syringes in order to minimize errors in dosing. Needle size/gauge to be used for IM injections should follow institutional guidelines and practice.

Total length of treatment will be 24 cycles. Each cycle will be 28 days +/- 5 days. Treatment will not be continued beyond 24 cycles.

Participants will be seen and monitored at the start of each cycle. A medication supply for up to a maximum of 33 days (28 + 5 days) will be dispensed.

If a participant misses a dose of medication on the scheduled day, a dose can be given up to 24 hours later. No injections should be given closer than 48 hours.

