14.2. Sample Size

Target is 20 patients for 16 evaluable participants.

To allow for 25% unevaluable participants, a maximum of up to 20 participants will be enrolled. We anticipate enrollment to be completed in 36 months with primary outcome measure defined in 12 months. The sample size for this trial is based on 3 primary factors: safety based on risk versus benefit. Sample size estimates were based on a single stage phase II clinical trial with the goal of demonstrating that the objective response rate of poly-ICLC is better than an objective response rate of a *poor* drug. For the sample size calculation, we assumed that the response rate of a poor drug (P_0) was 5% (i.e., $P_0 = 5\%$) and that the objective response rate poly-ICLC (P) would be at least 25% (i.e., $P = 25\%$).

In addition, the type I error rate (alpha) was set to 0.05 (5%) and the type II error rate ($\beta = 1 - \text{power}$) was set to 0.20 (20%). Using a single stage design, a sample size of 16 participants achieves at least 80% power to demonstrate that the objective response rate of poly-ICLC is better than a poor objective response rate of 5% and at least 25%. If the number of responders is 3 or more, the hypothesis that $P \leq 5\%$ is rejected with an actual error rate of 0.043. If the number of responses is 2 or less, the hypothesis that $P \geq 25\%$ is rejected with an actual error rate of 0.197. Sample size estimates were determined using PASS v. 19.0.2 (NCSS, LLC, Kaysville, UT).

Table 15: PASS Output Single-Stage Phase II Clinical Trials Analysis

Design for Testing $H_0: P \leq P_0$ versus $H_1: P \geq P_1$							
P_0	P_1	Alpha	Beta	Cut-Off $R + 1$	N	Actual Alpha	Actual Beta
0.05	0.25	0.050	0.2	3	16	0.04	0.197
Report Definitions							

P_0 is the maximum response proportion of a poor drug.P_1 is the minimum response proportion of a good drug.N is the sample size.If the number of responses $\geq R+1$, P_0 is rejected.If the number of responses $\leq R$, P_1 is rejected.Alpha is the probability of rejecting that $P \leq P_0$ when this is true.Beta is the probability of rejecting that $P \geq P_1$ when this is true.							

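### Table 14 counts patients as they enroll, with no event window, so its binomial hold probabilities are valid only if nearly all Grade 4 events occur early

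*Combined protocol and SAP*

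**What the plan says.** Section 12 (Safety Monitoring Criteria) says that Table 14 "defines the maximum allowed number of Grade 4 adverse events that are at least possibly attributable to the study drug". The rows are 5, 10 and 16 patients, with 1, 2 and 3 events permitted. Exceeding a limit places accrual on hold for review. The rows are tied to enrollment: "The table above gives the safety rule for each set of 5 participants that enrolls in the study", and the worked example reads "if 2 or more patients experience an event before the sixth patient begins therapy, the trial will be on hold".

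The Statistical Justification asks for a hold when the posterior probability that the event rate "exceeds 10% is equal to or higher than 0.95". It adds: "Safety rules were generated using a binomial distribution". On the printed figures it says "The third column gives the probability of holding enrollment on the trial when in fact, the true" rate is 0.10. Column 3 reads 0.081, 0.070, 0.068, and the cumulative column 0.081, 0.151, 0.219. No probability is given at any higher rate.

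Section 4.2 sets the exposure: "Total length of treatment will be 24 cycles. Each cycle will be 28 days +/- 5 days". Section 11.1 collects adverse events from enrollment until 30 days after the drug is stopped. Section 14.2 sets the pace: "We anticipate enrollment to be completed in 36 months with primary outcome measure defined in 12 months", with at most 20 enrolled.

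**The concern.** A binomial tail for 5 patients assumes that all 5 outcomes are known. Under an enrollment-based rule, the fifth patient may have been treated for only a few weeks when the sixth starts, and yet counts as one of five. The event rate has no time window, so a patient who has barely begun enters the row as event-free. If that patient has an event later, it is judged against a higher limit.

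The dilution, if there is any, is greatest in the first row, where a hold on accrual would spare the most children. Table 14 is the only numerical safety rule in the protocol, and the monitoring board would read its three-decimal probabilities as the rule's actual behavior.

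**Working it through.** **Inputs.** Looks at n = 5, 10, 16, with a hold at 2, 3, 4 or more events (Table 14). Stated rate 0.10 (section 12). Treatment 24 × 28 = 672 days, or 672/30.4375 = 22.1 months; one cycle is 0.92 months (section 4.2). Accrual of 20 patients in 36 months (section 14.2). My assumptions are even accrual (36/20 = 1.8 months per patient), 16 patients followed (the last row of the table), no dropout, at most one event per patient, and the onset patterns below. The 30% rate is also my choice, to represent a toxic drug.

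**Step 1: the plan's own figures.** At a rate of 0.10 the binomial tails are P(X ≥ 2 | 5) = 0.0815, P(X ≥ 3 | 10) = 0.0702 and P(X ≥ 4 | 16) = 0.0684. Column 3 is reproduced. The limits also agree with the 0.95 posterior criterion under a uniform Beta(1,1) prior (0.984 at 2/5, 0.981 at 3/10, 0.978 at 4/16), although the prior is not stated. The cumulative column is the plain sum 0.081 + 0.070 + 0.068 = 0.219. A trial already held at 5 patients cannot be held for the first time at 10. The first-crossing probabilities are 0.0815, 0.0318 and 0.0238, which sum to 0.137.

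**Step 2: exposure at each look.** When patient n+1 would start, patient i has been treated for t = 1.8 × (n − i + 1) months. At n = 5 that is 9.0, 7.2, 5.4, 3.6 and 1.8 months. On average patients have completed 24%, 45% and 65% of the 24 cycles at the three looks, and 0 of 5, 0 of 10 and 4 of 16 have finished treatment.

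**Step 3: first row with partial exposure.** Let events fall within the first W cycles, and let f = min(t / (0.92 W), 1). The chance that a patient's event has already occurred is p = θf (uniform onset) or p = 1 − (1 − θ)^f (constant risk). The hold probability is the chance of at least 2 events among five patients with unequal p.

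Example, θ = 0.30, W = 24, uniform onset: f = 0.408, 0.326, 0.245, 0.163, 0.082, so p = 0.122, 0.098, 0.073, 0.049, 0.024. Then P(0) = 0.681, P(1) = 0.275 and P(≥ 2) = 0.045. Constant risk gives 0.056.

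**Step 4: the whole rule at a true 30% rate** (200,000 simulated trials per scenario).

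| Onset spread over | First row | Any of three looks | Limits read at every event | Median enrolled at hold, limits read at every event |
|---|---|---|---|---|
| cycle 1 | 0.47 | 0.81 | 0.81 | 5 |
| 3 cycles | 0.43 | 0.79 | 0.80 | 5 |
| 6 cycles | 0.34–0.35 | 0.75–0.76 | 0.79 | 8 |
| 24 cycles | 0.04–0.06 | 0.41–0.44 | 0.76 | 16 |

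Ranges cover uniform onset and constant risk. The median of 16 is the ceiling of the model. If accrual took 12 months, the any-look figures would be 0.79 (cycle 1), 0.70 (3 cycles) and 0.03 (24 cycles, uniform).

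At the stated 10% rate the first-row value is 0.081 for cycle 1 onset, about 0.07 over 3 cycles, 0.05 over 6 and 0.005 to 0.006 over 24.

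**The case against.** The strongest answer is that everything turns on onset timing. Cycle 1 onset costs nothing, and onset over 3 cycles costs little (0.79 against 0.81 over the three looks). Section 6.6 describes flu-like reactions within hours that fade after the first few injections. It also describes edema after several weeks and enhancement changes at 3 to 6 months, so early onset is plausible but not established. None of this is an onset distribution for Grade 4 events. Section 2.4, on the earlier pediatric trial, was not in the text available to me and might contain one.

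Second, the hold criterion is not expressly confined to three dates, and section 14.3 promises continuous toxicity monitoring. If the limits are read at every event, a hold still comes in about 0.76 even with 24-cycle spread. This stands, and it removes most of the apparent loss in eventual detection. What remains is delay: a hold on accrual does little once 16 are enrolled.

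Third, a lower hold probability at 10% means fewer false holds and is not a harm. That is correct; only the higher rate bears on safety.

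Fourth, other safeguards exist. The research monitor reviews serious events and deaths and may stop the study (section 12), serious unexpected events are reported within 24 hours (section 11.5), and drug is interrupted for individual patients (section 6.4). These matter, but none adds a numerical rule or a follow-up requirement to Table 14.

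A reader might infer that the printed probabilities are simply wrong in practice and that a toxic rate will be found late. The documents do not support that, because they do not say when Grade 4 events occur.

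**Conclusion.** The point holds in conditional form. The rule counts enrolled patients while its probabilities assume complete outcomes, and the protocol states neither an event window nor the condition under which column 3 is valid. That mismatch is in the text and needs no assumption.

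Its size does need assumptions. At a true 30% rate with even 36-month accrual, the first-row hold probability lies anywhere from 0.47 down to 0.04, depending on onset. Eventual detection with limits read at every event changes much less (0.81 to 0.76), but the median number already enrolled goes from 5 to 16. The 24-cycle figures are an extreme and not a forecast. Quoting 0.41 to 0.44 as the rule's performance would require both that spread and a restriction to three looks.

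The cumulative 0.219 is a separate arithmetic error that depends on no onset assumption: with full observation it should be 0.137.

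**What to change.** In section 12, define the event rate as the probability of a qualifying event within a fixed number of cycles, chosen by the sponsor and short relative to accrual. Let a patient count toward a Table 14 row only after completing that window or having an event. Let every event count at once, including events after the window.

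Then recompute the hold probabilities by simulation under that exact rule and the planned accrual, at 10% and at one or more higher rates, and replace columns 3 and 4 with the results. State the onset assumption used. Do not add a note that the present column 3 applies. Counting events at once while event-free patients wait brings events into a row sooner, so the rule is no longer a plain binomial. At a 10% rate the first-row hold probability under this rule is about 0.09 with a 3-cycle window and onset, 0.11 with 6 and 0.27 with 24, against 0.081 printed.

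The cost is protocol wording, one table and a short simulation. Rows are reached later: a 3-cycle window is 3 × 0.92 = 2.8 months, or about 1.5 patients of accrual, and a 6-cycle window is 5.5 months, or about 3 patients. A 24-cycle window would delay rows by about 22.1/1.8 = 12 patients, which is why a short one is needed. False holds for review rise slightly with a 3- to 6-cycle window. No dose or treatment rule changes.
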